4. PROCEDURES

UMTRI will begin the initial data collection starting with older children, which is why the IRB-approved materials and instruments provided currently focus on the older age range. The full age range of the study is children 3 months to 5 years of age.

Appendix A provides an example of how the OMB Control Number will be displayed on materials provided to participants. All time calculations have been included in the burden estimates provided in Supporting Statement A.

1. At UMTRI, a research assistant will explain and demonstrate the procedures to the caregiver and child. Written consent will be obtained from the caregivers, who will remain with the children at all times. Researchers will obtain verbal assent from the children who are old enough to provide it. An example of the written consent is provided,

- called Research Study Consent. This consent form references the age range 18 to 71 months, and after the initial data collection, the form will be amended to include children who are 3 months and older.
- 2. Researchers will obtain several standard anthropometric measurements from each child, including body weight and erect standing height. For bite strength participants, researchers will record mouth breadth and maximum mandibular opening.

 Anthropometric measures will allow the data to be normed to the U.S. population using anthropometric data from NHANES (CDC).
- 3. Researchers will record the participant's body shape using a whole-body laser scanner (VITUS XXL) and a Microsoft Kinect sensor. The research team has used both of these systems in several previous child studies. The laser scanner captures a high-resolution image of the subject's body shape in about 12 seconds. The Kinect will be used to capture the force-exertion postures. The laser-scan data will be used to create a subject-specific avatar that is used to aid posture tracking with the Kinect. The posture data are valuable to characterize the tactics that the children use for each exertion.
- 4. In the laboratory, the children will perform a sequence of tasks to test maximal exertions with their hands and feet. For standing tasks, they will grip a padded handle with one or both hands, as instructed, and push or pull as hard as they can. Each exertion will be targeted for approximately 5 seconds, including the ramp-up and release. Feedback will be provided to the participants via a graphic display that shows their maximum level achieved, so that they can be encouraged to go beyond that level, if possible. For bite strength, children will bite on a bite dynamometer that is fabricated to suit the age cohort.
- 5. For some trials, the participant will be seated in a specially constructed laboratory chair. Seated exertions will include pushes and pulls with the hands and pushes with one and both feet. Conditions will be varied to avoid loading up one part of the body consecutively. For example, a hand pull might be followed by a hand or foot push. Researchers will determine the trials to be performed, based on the result of previous pilot testing and the ability of the child. For example, if researchers have already established that children 36 months and up can reliably perform standing two-hand pushes, they will choose different types of exertions with subsequent subjects.
- 6. Researchers will record video and still images of the trials. The video and images will be used by the research team to assess the children's performance, particularly their tactics for achieving the requested exertions. This information will be valuable for developing the measurement protocols.
- 7. Trials will be separated by a minimum of 15 seconds to allow time for recovery. Longer recovery time is anticipated to be impractical, due to a loss of attention from the child;

but switching between limbs and exertion directions will reduce fatigue. The caregivers will be engaged in every step of the process, including directing and encouraging the children.

- 8. The number of trials to be performed will depend on the capability and attention of the child, but the maximum duration of a child's participation in a single session will be 2 hours. A 5-minute break will be taken at least every 20 minutes, to allow the child to relax and play. The caregiver and child can take a break, or discontinue participation, at any time.
- 9. The caregiver will be paid an incentive of \$40 for up to 2 hours of participation.
- 10. Photos and video of the participants will be taken in some conditions to document their exertion postures. The researchers will de-identify the photos by blurring or obscuring the faces.

5. DESCRIPTION OF METHODS TO MAXIMIZE RESPONSE RATE AND TO DEAL WITH NON-RESPONSE ISSUES

To reduce the number of no-shows, researchers will send scheduled participants a reminder letter and/or call them on the telephone, giving the time of the session and directions to the location.

Researchers will provide \$40-\$50 compensation for up to 2 hours of participation, as an incentive to participate in the experiment. Additional detail on the importance of compensation is provided in Supporting Statement A.

6. DESCRIBE ANY TESTS FOR PROCEDURES OR METHODS TO BE UNDERTAKEN

The Child Strength Study will be based on convenience sampling and is not intended to be a representative sample to accurately reflect the characteristics of the children living in the United States. The sampling technique and sample size for the proposed study is consistent with previous child strength studies. These data have been used to draw inferences about the strength capabilities of children in the United States. To address the limitations of convenience sampling and ensure the representativeness of the study, UMTRI will use statistical methods to relate the measures strength to child age, as well as anthropometric factors that vary with age, such as body weight and standing height. This will allow the data to be normed to the U.S. population using anthropometric data from NHANES (CDC).

Initial pilot testing has been conducted, and an additional pilot study will be conducted to refine the data collection procedures and instruments, followed by the full study. Because this pilot is designed solely to test the study methods and not for analysis of the data, researchers will select the pilot participants.

COVID-19 Mitigation

UMTRI researcher have developed a safety protocol to include COVID-related precautions. UMTRI researchers are required to adhere to guidance from the University of Michigan Office of Research concerning human subject testing. The Office of Research has issued guidance for human research during the pandemic, which is available on their website (https://research.umich.edu/covid-19/human-research-during-covid-19/); this guidance is updated regularly to address changing health and safety measures. As of December 2021, the University of Michigan requires research team members to wear a face covering when conducting face-to-face interactions with human research participants; University of Michigan faculty, staff, and students are required to receive the COVID-19 vaccination. The ability to conduct human subjects testing will be based on local conditions and applicable mandates. CPSC has reviewed the risk-mitigation protocols recommended by the Office of Research and implemented by UMTRI, and the Child Strength Study will proceed only on the basis that these mitigation protocols will be adhered to.

One purpose of the Child Strength Study is to update and expand child strength data with a focus on real-world scenarios. Researchers at UMTRI are hopeful that they can conduct the Child Strength Study without any COVID-related restrictions on how the child participant interacts with the test fixture or the investigators (masks for the investigators and caregivers would be fine). There are some measures in the study, for example bite strength, for which it would be very difficult or impossible to collect meaningful data with the restrictions currently in place. If restrictions are still in place when it is time to collect data, researchers and CPSC staff will make decisions on what measures can be collected without compromising the real-world applicability of the data, and will modify the list of measures as needed. This is because it would not be worthwhile to gather this important data, which is intended to have long-term archival value, with the condition of it being collected during a pandemic. Data that are compromised by the COVID pandemic or protocols are not worth collecting at this time.

7. PROVIDE NAME AND PHONE NUMBER OF INDIVIDUALS CONSULTED ON STATISTICAL ASPECTS OF STUDY DESIGN AND OTHER PERSONS WHO WILL COLLECT/ANALYZE INFORMATION FOR AGENCY

[name]. [contact]. Research Professor and Head Biosciences Group, University of Michigan Transportation Research Institute (Collect and Analyze)

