Maximal occlusal bite force for children in different dentition stages were recorded in a large-scale study (Owais et al. 2013). Children were stratified across the range of dentition stages and ages 3 to 18 years. Two hundred children were measured within each dentition stage. Bite force was quantified alternatively on the right and left side, positioned at the second primary or the first permanent molars region. A portable occlusal force gauge was used, consisting of a hydraulic pressure gauge and bite element encased in a vinyl material. Maximal bite forces differed significantly across the dentition stages, increasing with age. Age, gender and height were found to be significant predictors of bite force at the later stages of dentition.

Conflicting evidence persists in defining the relationship between bite force and sex, age, size and physical characteristics of children. The variability of bite force data is considerable, with numerous factors influencing these results. To address this debate, Singh, Sandhu, and Kashyap (2012) investigated the relationship between bite force and facial morphology, classified by malocclusion groups, for children ages 12 to 16 years. Bite force was measured at intercuspal position and anterior bite position. No significant differences were observed between the classes of malocclusion.

Recently, Verma et al. (2017) published a comprehensive overview of bite force transducers, covering both custom devices used in research and commercially available systems. Many of the systems have limited applicability to child bite force measurement, due to the relatively large sizes (many more than 10 mm thick).

With guidance from the literature, the research team for the proposed study plans to fabricate a bite dynamometer suitable for measurements with young children. The dynamometer should enable measurement of maximum and sustained incisal and buccal bite strength, will be capable of being sterilized, and will be covered with sterile, disposable, non-allergenic material before measurement of each participant.

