2. DESCRIPTION OF SAMPLING METHOD TO BE USED

The research team at UMTRI will collect data from approximately 800 children for the study.

A convenience sampling method will be used. The population of interest is children ranging in age from 3 months (bite strength) or 6 months (exertions with hands and feet) through 5 years. Participants for older age group ranges will be recruited first, followed by younger participants later in the study. They will be recruited via their caregivers through the University of Michigan Engage site, Craigslist, and flyers placed at UMTRI. The participants will be screened via a phone conversation with the caregiver. Inclusion criteria will include: the targeted age group; lack of current illness or injury; age appropriate cognitive and motor development, as reported by the caregiver; and the caregiver's ability to understand written and spoken English (older children should also understand spoken English).

3. DESCRIPTION OF PROCEDURES FOR INFORMATION COLLECTION, INCLUDING STATISTICAL METHODOLOGY FOR STRATIFICATION AND SAMPLE SELECTION

The target number of participants per age group in the proposed study (50 children) is the same as that used in Brown, Buchanan, and Mandel (1973, 1974), and it is larger than the number used in Owings et al. (1977), U.K. Department of Trade & Industry, Government Consumer Safety Research (2000), Reus et al. (2013), and studies referenced in Norris and Wilson (1995). In

addition, the proposed study has narrow age bands, to allow more precision in assessing child strength by age.

The data gathered in this study will be used for a wide range of purposes, some foreseen and others that will arise in the future. Thus, as an exploratory research study, it is not possible, or sensible, to specify a necessary level of precision for any estimates of population distribution parameters. A calculation of sample size, using data from a previous strength study and a potential confidence bound, is shown below, assuming the sample size criteria were met.

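### Norming strength on age and body size cannot ensure representativeness, as section 6 claims; it aligns the sample with U.S. children on those variables only

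*Protocol*

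**What the plan says.** Section 2 (sampling method): "A convenience sampling method will be used". On the channels: "They will be recruited via their caregivers through the University of Michigan Engage site, Craigslist, and flyers placed at UMTRI". Children must be in the target age group and free of illness or injury at the time. The other criteria include "age appropriate cognitive and motor development, as reported by the caregiver" and "the caregiver's ability to understand written and spoken English".

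Section 6 (tests for procedures or methods) says of the study that it "is not intended to be a representative sample to accurately reflect the characteristics of the children living in the United States". Two sentences later the same paragraph reads: "To address the limitations of convenience sampling and ensure the representativeness of the study, UMTRI will use statistical methods". The methods relate strength to "child age, as well as anthropometric factors that vary with age, such as body weight and standing height", and the paragraph says that this lets the data be normed to the U.S. population with NHANES anthropometry. Section 4, item 2 repeats the norming statement.

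No other adjustment or weighting variable is named in the protocol.

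**The concern.** The paragraph disclaims representativeness for the sample and then promises it for the study, with modelling as the bridge. A model in age, weight and height can carry results from the sample to the U.S. only along those variables. The ways in which children enter this study are not confined to them, and the protocol does not state the assumption that would make the bridge hold.

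The wording matters because of how the data may be used. Section 6 notes that data from earlier studies of this kind have supported inferences about U.S. children. Section 3 expects many uses, some not yet foreseen, and section 6 speaks of archival value. A later user could read the promise as a guarantee that the normed values hold for U.S. children in general.

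**Working it through.** **1. The plan's only calculated figure.** Section 3 takes a COV of 0.4 and a mean of 40 N, so SD = 0.4 × 40 = 16 N. For 95% confidence and ±2 N:

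n = (1.96 × 16 / 2)² = 245.85, rounded up to 246.

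This agrees with the protocol. The 95% half-width, 1.96 × 16 / √n, is 6.27 N at n = 25, 4.43 N at the target of n = 50, and 2.00 N at n = 246. This calculation covers sampling error only. The present point does not depend on it and does not change it.

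**2. What norming delivers.** Let Y be strength, X age and body size, and R = 1 for a recruited child.

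- Target mean: the average of E[Y | X] over the U.S. distribution of X.
- Normed mean: the average of E[Y | X, R = 1] over the same distribution.
- Remaining bias: the average of E[Y | X, R = 1] − E[Y | X] over that distribution.

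The bias is assured to be zero only if recruited and non-recruited children of the same age and size have the same mean strength. Percentiles need the same condition for the whole conditional distribution. The sample size n does not appear in the bias, so recruiting more children shrinks the half-width in step 1 but leaves this term unchanged.

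**3. Routes of selection set against the norming factors.**

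| Route of selection (section 2) | Covered by norming on age and body size? |
|---|---|
| Age group | Yes |
| Weight or height differing from the U.S. | Yes |
| University site, classifieds site, flyers at the institute | Only as far as it acts through age or size |
| No illness or injury at the time | Only as far as it acts through age or size |
| Age-appropriate cognitive and motor development | Only as far as it acts through age or size |
| Caregiver understands English | Only as far as it acts through age or size |

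Screening on motor development is the clearest case in which selection could act on strength at a given size. The protocol gives no data on whether it does, or by how much.

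**4. Check of the mechanism by simulation, on assumed values.** None of the selection inputs below is in the protocol.

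- Strength has mean 40 N and rises 8 N per SD of body size.
- The sample is 0.3 SD larger than the population.
- A second, unmeasured factor with two levels shifts strength by b at a given size. Its prevalence in the sample differs from the population by Δ.

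With Δ = 0 the raw bias is about 8 × 0.3 = 2.4 N, and norming on size reduces it to about 0. With Δ above 0, norming leaves b × Δ. For b = 4 N and Δ = 0.1 this is 0.4 N (simulated 0.41). For b = 8 N and Δ = 0.4 it is 3.2 N (simulated 3.23). Norming therefore does its own job and no more. These values show the mechanism and do not estimate the bias in this study.

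**The case against.** **The two statements can be reconciled.** The first describes the sample and the second describes adjusted results. Standardising a non-representative sample is a coherent practice, and the limitation is disclosed in the same paragraph. This stands, and it means that the point is not a plain contradiction. What remains is the verb: the method can standardise for named variables, but it cannot ensure representativeness.

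**The factor list is open, and an analysis plan may say more.** The factors are introduced as examples, and a full covariate list may properly sit elsewhere. This also stands, so an incomplete list is not the complaint. The list is, however, open only to anthropometric factors that vary with age. Recruitment channel, language and health screening are not of that kind. The complaint concerns an affirmative claim in the protocol.

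**Stronger readings that the protocol does not support:**

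- *Sex is wrongly left out.* A reader might infer this from section 1: "Age, gender and height were found to be significant predictors of bite force at the later stages of dentition". That result concerns bite force only, at later dentition stages, in a study of ages 3 to 18 years. The next paragraph of section 1 calls the evidence on sex and bite force conflicting. Sex is not named in the sampling, measurement or norming text, but nothing shows that it is excluded or that it predicts strength at these ages.
- *The bias is of a known, serious size.* Taking bias as 100 × 0.40 × d × √(1 − R²) per cent of the mean, with assumed R² of 0.2 to 0.5, gives 7.1% to 8.9% for d = 0.25 and 14.1% to 17.9% for d = 0.5. The assumptions in step 4 of the working give 0.4/40 = 1% to 3.2/40 = 8%. The overall spread of about 1% to 18% reflects only the chosen inputs. Nothing in the protocol shows that selection bias rivals the half-width of 4.43 N (11% of 40 N).
- *Normed values will be published as U.S. distributions with intervals for sampling error only.* The protocol states no such publication rule and no interval method for normed values.

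**Conclusion.** The point holds in a limited form. Section 6 credits the study with a property that its design does not have. Norming on age and body size aligns the sample with U.S. children on age and body size. Anything beyond that rests on an unstated assumption: that recruited and non-recruited children of the same age and size are equally strong. The recruitment and screening in section 2 give reason to doubt this assumption but do not show that it fails.

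The size and direction of any remaining bias are unknown from the protocol, and more children would not reduce it. The protocol calls the study exploratory and not powered for hypothesis tests. No stated number is wrong on this account, so this is a correction to a claim and to the population it covers.

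**What to change.** 1. In section 6, replace the promise to ensure representativeness with: *standardise the results to the U.S. distribution of age and body size*.
2. State the assumption: recruited and non-recruited children of the same age and size have the same strength. Add that selection on other factors is not corrected.
3. State that results apply to children who meet the section 2 criteria.
4. Report unadjusted values beside normed values, so that readers can see what the norming changed.
5. Optionally, record sex and include it in the norming model. This is a reasonable precaution and does not repair a demonstrated error.

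Items 1 to 3 change wording only, and item 4 adds a column to the results tables. The price is a less favourable claim. No stated number or sample size changes.
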